17.3 ISEE2009 Study Schematic

 IVT avacincaptad pegol 2 mg  No Study Injection

*Patients who completed Study ISEE2008 through Month 24 (regardless of treatment arm)

17.4 Protocol Amendment Summary of Changes

DOCUMENT HISTORY	
Protocol Version	Protocol Version Date
Protocol Amendment 01	27 February 2024
Protocol Amendment A (France)	28 November 2022
Original Protocol	27 July 2022

Amendment 01 dated 27 February 2024

This amendment is considered to be substantial based on the criteria set forth in Article 10(a) of Directive 2001/20/EC of the European Parliament and the Council of the European Union and EU Clinical Trial Regulation.

Overall Rationale for the Amendment:

The primary purpose of this amendment is to update the sponsor and to apply clarifications to the conduct of the study throughout the protocol.

Substantial Changes

Section # and Name	Description of Change	Brief Rationale
Throughout	The sponsor is updated from Iveric bio to Astellas Pharma Global Development (Astellas).	To reflect the change in sponsor.
2; 6; 8.1	The approximate number of subjects to be enrolled is reduced from 400 to 280	To update the number of subjects expected to complete the ISEE2008 study and be eligible to enroll in ISEE2009, based on current data.

2; 5.2; 11.1	
Study safety endpoints clarified as follows:
 
Primary Endpoint:
 
 • Adverse Events (AEs) 
Secondary Endpoints:
 
 • Immunogenicity • Pharmacokinetics 
Exploratory Endpoints:
 
 • Ophthalmic findings (BCVA, LLVA, IOP, and ophthalmic examination) 	To specify primary, secondary, and exploratory endpoints of existing endpoints as required. Study endpoints were originally specified only as “safety endpoints”.
--------------	--	---

Nonsubstantial Changes

Section # and Name	Description of Change	Brief Rationale
Title Page	Regulatory agency identifier numbers are added.	To include regulatory agency identifiers as required.
Title Page	Sponsor confidentiality statement is updated.	To provide updated confidentiality statement per change in Sponsor.
2; 6; 9.1.2; 10.6	Removal of market authorization of study drug and commercial availability as reason for premature study termination	To reflect that commercial availability of study drug does not impact study duration.
2; 11.2	The justification for sample size is updated	To clarify that the sample size is based on enrollment and eligible subject completion in ISEE2008

3; 10.2	Specified “as applicable” for ocular assessments at Month 12 and Month 18 performed pre-injection on both eyes (OU)	To provide clarity on pre-injection ocular assessments, given that there is no injection at Month 18
3	A cross-reference to Appendix 17.1 for details on procedures for refraction and vision testing is added.	To ensure understanding of study procedures.
3; 10.2	The requirement to perform a full ophthalmic evaluation at 0 to 5 minutes post-injection is revised to an abbreviated exam.	An abbreviated exam is adequate to monitor health of eye immediately post-injection.
3; 7.2; 10.2	The timepoints for performing Goldmann applanation tonometry are updated to pre- and post-injection as applicable.	To clarify the timepoints when this assessment is to be conducted.
4.1	Deletion of concluding paragraph of Section 4.1 GA Disease State Overview	To align with current state of unmet medical need
4.1.2	Revision of Section 4.1.2 Unmet Medical Need	To align with current state of unmet medical need
4.2	Description of avacincaptad pegol is updated	To align with description in current IB
4.4	Updates to Section 4.4 Completed and Ongoing Clinical Trials	To reflect current information

4.5	Clinical data cited in the trial rationale is updated to reflect current information.	To provide current information.
4.6	A benefit/risk assessment is added.	To summarize the benefits and risks of avacincaptad pegol based on current clinical data, and to meet the requirements of European Clinical Trial Regulation. The data in the benefit/risk assessment is updated but the overall benefit/risk ratio is not significantly changed compared to the benefit/risk statement in the most recent IMPD.
6	Added statement “This is an open-label, multicenter 18-month extensions study.”	For clarity on trial design and length of study
6; 10.6	The end of trial definition is added.	To provide a clear definition of the end of the trial.
9.1.1	Avacincaptad pegol composition details updated	For clarity and consistency with program level documents
9.2	The exclusion of previous treatment for CNV in study ISEE2008 is removed.	To align with current requirements for study ISEE2008. Subjects treated for CNV in ISEE2008 are eligible for enrolling into ISEE2009.
9.2	The exclusion of any treatment with investigational agent(s) during the trial is removed.	Placed in tabular format in Section 9.2.1
9.2.1	A table listing prohibited medications is added.	To specify prohibited medications. Prohibited medications was absent from the original protocol
10.1; 13.4	References to waivers from individual protocol criteria are updated to clarify that waivers to the protocol, including inclusion and exclusion criteria, are not allowed.	To preserve trial integrity.

10.3	Vabysmo® (faricimab) is added as a treatment option for CNV.	To reflect additional treatment option for CNV.
10.4	Treatment failure is added as an event qualifying for withdrawal from trial.	Subjects with treatment failure should be withdrawn from trial to avoid continued exposure to ineffective treatment.
10.5	Study drug discontinuation section is added to describe circumstances when a subject may discontinue study treatment but remain on trial for safety evaluation.	To continue to monitor safety of the subject and collect safety data in case of early discontinuation of study treatment.
10.6	Added subject study completion definition to the Section describing Trial Discontinuation.	To clarify the definition of completed subject for analysis purposes.
11.6	New section Interim Analysis with reference to the SAP for details on interim analysis is added.	The full description of interim analysis details is provided in the SAP as applicable.
12.3	Adverse Events of Special Interest are updated as follows: 
 • Endophthalmitis • Ischemic optic neuropathy • Intraocular inflammation; any case of uveitis, retinal vasculitis or retinal vascular 	To add clarity to AESI definitions for the Investigator and to aid in management of AESI reporting; Ischemic optic neuropathy added as a new AESI to reflect current events included in safety signal monitoring.

	
occlusion occlusive vasculitis
 
 • IOP \geq 30 mmHg at 30 minutes post injection deemed clinically significant by the investigator • Transient vision loss of light perception immediately after injection • Elevation of IOP post-injection requiring surgical/procedural intervention (i.e., paracentesis; for instruction regarding paracentesis refer to Appendix 17.2) • BCVA decrease \geq30 letters from Screening in the ISEE2009 Month 1 Visit • CNV (exudative or nonexudative) in the SE 
Clarification of AESI handling for study eye versus fellow eye is also added.
	
--	---	--

2.0	See the signature page	3.1	Low Luminance Deficits (LLD) and Geographic Atrophy (GA) area will be summarized over Full Analysis Set.	LLD is considered as a variable of interest. Adding LLD and GA area is for completeness of the description.
		4.2.3	Baseline LLD is added as a variable to be summarized for visual acuity.	LLD is considered as a variable of interest.
		4.2.3	List of baseline Fundus Autofluorescence (FAF) measurements to be summarized were added.	For clarification of the baseline FAF measurements to be summarized.
		4.2.3	“Fluorescein angiography (FA) imaging assessment” is removed from baseline characteristics to be summarized	This variable at baseline was not collected per protocol.
		4.4	“Positive” is added to the definition of “Total Positive” in Table 1.	“Positive” was previously missing in the definition of “ADA Total Positive”.
		4.4	Swimmer plot for ADA total positive participants’ experience of ocular TEAE is removed.	Analysis with limited add-on value due to anticipated small number of ADA total positive participants.
		4.5	Pre-injection IOP and post-injection IOP definitions are updated.	For clarification in the definition of pre-injection IOP and post-injection IOP.
		4.5	Mean of pre-injection IOP change from baseline and post-injection IOP change from pre-injection will be plotted instead of pre-injection IOP and post-injection.	To support visualization of the IOP related analysis with more interests.

SAP Version	Approval Date	SAP Section(s)	Change	Rationale
		4.5	LLD will be summarized by visit over Full Analysis Set.	LLD is considered as a variable of interest.
		4.5	A subtitle is added for Geographic Atrophy Area	The subtitle was previously missing.
		4.6.1	Change the category name of “systemic” TEAE to “non-ocular” TEAE for the additional TEAE overview table.	Consider “non-ocular” is a more appropriate name comparing to “systemic”. There is no change in the derivation/interpretation.
		4.6.1	Serious non-ocular TEAEs, Serious Study drug related non-ocular TEAEs, and Serious injection procedure related non-ocular TEAEs will be summarized by SOC and PT.	These TEAEs are of interest.
		4.6.1	TEAEs with frequency of $\geq 2\%$ in any cohort, Ocular TEAE with frequency of $\geq 2\%$ in any cohort, and Non-ocular TEAE with frequency of $\geq 2\%$ in any cohort will be summarized by PT.	The TEAEs with frequency of $\geq 2\%$ are considered as common and of interest.
		4.6.1	Variables in the listings are updated.	For clarification without any change in meaning.
		4.6.2	“Macular oedema/cysts” is added as an AESI.	Alignment at ACP project level.
		4.6.2	Point out AESI are TEAEs on study eye.	For clarification and align with protocol.
		4.10.1	Additional Rules for OE/IOP Analysis Flags except those in the Analysis Visit Month 18 are updated.	For clarification and including unpaired IOPs into the summary at each analysis visit.
		Throughout SAP	Corrected topographic errors and edits without changing contents.	To improve clarity and correct errors.

1 INTRODUCTION

This Statistical Analysis Plan (SAP) contains technical and detailed elaboration of the principal features of the analysis described in the protocol and includes procedures for executing the statistical analysis to fulfil the objectives of the study.

The final SAP will be approved prior to database lock.

If there are any changes from the planned analyses in the final version of the SAP that impact the statistical analyses, then it will be documented in the Clinical Study Report.

1.1 Objective and Endpoints

The objectives of this trial are to assess long-term safety of avacincaptad pegol intravitreal administration for patients with geographic atrophy (GA) who completed Study ISEE2008 (GATHER2) through the Month 24 visit on study treatment (either avacincaptad pegol or Sham).

The endpoints include below:

- Primary Endpoint
 - Adverse events (AEs),
- Secondary Endpoints
 - Immunogenicity,
 - Pharmacokinetics,
- Exploratory Endpoints
 - Ophthalmic variables
 - ◆ best corrected visual acuity (BCVA),
 - ◆ low luminance visual acuity (LLVA),
 - ◆ intraocular pressure (IOP),
 - ◆ ophthalmic examination (OE).

1.2 Study Design

This is a Phase 3, Open-label Extension study to evaluate the long-term safety of avacincaptad pegol (ACP). Approximately 280 patients who completed Study ISEE2008 (GATHER2) through the Month 24 visit on study treatment (either ACP or Sham) and consent to participate will be administered monthly ACP 2 mg from Month 1 through Month 17 (maximum seventeen total doses).

All patients will have a final follow up visit at Month 18 or if the study is terminated early, Month 18 final follow up procedures will be followed. Premature termination of this clinical trial may occur because of a regulatory authority decision, change in opinion of the Institutional Review Board/Ethics Committee, or at the discretion of Astellas.

Details of the schedule of clinical assessments are available in the protocol.

1.3 Randomization

This is an open-label study and no randomization applied.

2 STATISTICAL HYPOTHESES

No statistical hypotheses will be tested.

3 ANALYSIS SETS

In accordance with International Conference on Harmonization (ICH) recommendations in guidelines E3 and E9, the following analysis sets will be used for the analyses.

3.1 Full Analysis Set

The Full Analysis Set (FAS) consists of all enrolled participants. The FAS will be used for the patient disposition, summary of demographics and other baseline characteristics, and analyses of GA area, BCVA, LLVA and LLD in this study ISEE2009.

3.2 Safety Analysis Set

The Safety Analysis Set (SAF) consists of all treated participants, i.e., those received at least one administration of study drug.

The SAF will be used for the analysis of safety endpoints. When all enrolled participants have been treated, the SAF is identical to FAS.

3.3 Pharmacokinetic Analysis Set

The pharmacokinetic analysis set (PKAS) consists of all treated participants with at least one valid plasma concentrations result. Additional participants may be excluded from the PKAS at the discretion of the pharmacokineticist.

The PKAS will be used for PK analysis.

3.4 Anti-drug Antibody (ADA) Analysis Set

The ADA analysis set (ADAAS) consists of all treated participants with at least one valid ADA result.

The ADAAS will be used for immunogenicity analysis.

4 STATISTICAL ANALYSES

4.1 General Considerations

Continuous data will be summarized descriptively including the number of participants (n), mean, standard deviation (SD), median, minimum, Q1, Q3 and maximum. Categorical data will be summarized descriptively by frequencies and percentages. Percentages by categories will be based on the number of participants with no missing data, i.e., the percentages for the non-missing categories will add up to 100%. Participants with missing data are generally not included unless otherwise specified. When needed, the category of 'Missing' is created and the number of participants with missing data is presented.

All data summarization and analyses will be performed using SAS® Version 9.4 or higher on Red Hat Enterprise Linux. Specifications for table, figures, and data listing formats can be found in the Tables Listings Figures (TLF) specifications.

Summaries will be presented for the following cohorts unless otherwise specified:

- ACP EM to ACP EM, including all participants who received ACP every month (EM) through the Month 24 visit in the parent study ISEE2008 and enrolled in this study,
- ACP EM/EOM to ACP EM, including all participants who received ACP EM through the Month 11 visit and then randomized to ACP at Month 12 and administered ACP every other month (EOM) at Months 13, 15, 17, 19, 21, 23 in the parent study ISEE2008 and enrolled in this study,
- ACP to ACP EM, including all participants who received ACP EM through the Month 11 visit and then ACP EM or EOM through the Month 24 visit in the parent study ISEE2008 and enrolled in this study, which is the combination of the above two cohorts,
- Sham to ACP EM, including all participants who received Sham through the Month 23 visit in the parent study ISEE2008 and enrolled in this study,
- Total, including all participants who enrolled in this study regardless of the study drug and frequency they previously received in the parent study ISEE2008.

Baseline values will be defined as the last available value prior to the first administration of study drug in this study ISEE2009, unless otherwise specified.

4.2 Study Participants

Participant disposition, protocol deviations, demographics and other baseline characteristics and previous and concomitant medications will be summarized descriptively and listed for the FAS. Extent of exposure analysis will be based on the SAF.

4.2.1 Participant Disposition

Disposition of participants will be summarized for the FAS. Number and percentage of participants who complete or prematurely discontinue from the treatment or study will be summarized by cohort. For discontinuation, the primary reason reported by the investigator will be summarized by cohort.

4.2.2 Protocol Deviations

All protocol deviations will be assessed and identified prior to database lock to determine whether they are major or minor by the sponsor. The final list of major protocol deviations will be provided prior to the database lock.

The major protocol deviations will be summarized by cohort for the FAS. In the summary table, participants deviating from a criterion more than once will be counted once for the corresponding criterion. Any participants who have more than one major protocol deviation will be counted once in the overall summary. The details will be provided in a participant listing.

4.2.3 Demographic and Other Baseline Characteristics

Demographics will be summarized descriptively by cohort for the FAS. The variables to be summarized include but not limited to:

- Sex,
- Age, Age Categories (50 to <65, 65 to 74, 75 to 84, ≥85), European Union Drug Regulating Authorities Clinical Trials Database (EudraCT) age categories (<65, ≥65 to <85, ≥85),
- Race,
- Ethnicity.

Other baseline characteristics of SE will be summarized descriptively by cohort in separate tables. These baseline characteristics include the followings:

- Visual acuity, including but not limited to BCVA (Early Treatment Diabetic Retinopathy Study [ETDRS] letters), LLVA (ETDRS Letters) and LLD,
- Ophthalmic exam (OE), including but not limited to motility, lids/lacrimonal/lashes, conjunctiva/sclera, cornea, anterior chamber activity, cells, iris, pupils, lens status, vitreous haze, vitreous hemorrhage, posterior vitreous detachment, optic nerve, macula, retinal vessels, and peripheral retina,
- Tonometry,
- Fundus Autofluorescence (FAF) imaging measurements, including but not limited to localization of hypo FAF, multifocal geographic atrophy, temporal peripapillary atrophy, area of geographic atrophy and size of geographic atrophy.

A listing of demographic and other baseline characteristics will be provided.

Prior ocular history is defined as all ocular events prior to the first administration of the study drug in this study, including the prior ocular history events of the parent study ISEE2008.

The prior ocular history is coded in Medical Dictionary for Regulatory Activities (MedDRA) and will be summarized by System Organ Class (SOC) and Preferred Term (PT), by cohort, for Study Eye (SE) and Fellow Eye (FE) separately. A listing of prior ocular history will also be provided.

Medical history (excluding ocular history) is defined as all non-ocular medical events prior to the first administration of the study drug in this study, including the non-ocular medical history events of the parent study ISEE2008. The medical history (excluding ocular history) is coded by MedDRA, and will be summarized by SOC and PT, by cohort. A listing of medical history will also be provided.

Prior surgeries/procedures are defined as all surgeries/procedures prior to the first administration of the study drug in this study, including any prior or concomitant surgeries/procedures recorded in the parent study ISEE2008. The prior surgeries/procedures are coded by MedDRA, and will be summarized by SOC and PT, by cohort. A listing of prior surgeries/procedures will also be provided.

4.2.4 Previous and Concomitant Medications

Previous medications are defined as any medications that participants started prior to the first administration of the study drug in this study, including the medications that started before and during the parent study ISEE2008.

Concomitant medications are defined as any medications that participants took after the first administration of the study drug in this study and through the last follow-up visit in this study. Medications that started prior to and continued after first administration of study drug in this study will be counted in both previous and concomitant medications.

Previous and concomitant medications will be summarized separately by therapeutic subgroup (anatomical therapeutic chemical (ATC) 2nd level), chemical subgroup (ATC 4th level), preferred world health organization (WHO) name (active ingredients for combination drugs) and cohort for the FAS. Participants taking the same medication multiple times will be counted once per medication. A medication which can be classified into several chemical and/or therapeutic subgroups is presented in all chemical and therapeutic subgroups.

4.2.5 Extent of Exposure

The following variables of exposure will be descriptively summarized by cohort for the SAF:

- Treatment duration (months) defined as (last injection date – first injection date + 31)/30.4375,
- Total number of injections received.

4.3 Primary Endpoint(s) Analysis

The primary endpoint is AEs. Analysis on AE will be described in Section 4.6.

4.4 Secondary Endpoint(s) Analysis

The secondary endpoints include immunogenicity and pharmacokinetics. All the assessments will be mapped to an analysis visit. The mapping rule is provided in Table 4.

Immunogenicity

ADA status (either positive or negative) will be evaluated by ADA against ACP, ADA against aptamer and ADA against Polyethylene glycol (PEG) for each ADA sample.

The following ADA incidences will be summarized over the ADAAS in total. A listing of ADA results will also be provided. Baseline value is the last available value prior to the first administration of study drug in this study ISEE2009.

Table 1 Definition of the ADA Incidences

ADA Incidence	Definition
Baseline and at least one post-baseline status	Number of participants with valid baseline and at least one post-baseline ADA results
Baseline negative	Number of participants with a negative ADA status at baseline
Post-baseline positive, who were negative at baseline	Number of participants with a negative baseline and at least one positive post-baseline ADA status
Baseline positive	Number of participants with a positive ADA status at baseline
Post-baseline positive	Number of participants with at least one post-baseline positive ADA status
Treatment boosted positive	Number of participants with an at least one post-baseline ADA increase from a positive baseline ^a
Total Positive	Total number of participants who are either with a negative baseline and at least one post-baseline positive ADA status, OR treatment boosted positive
Total Negative	Total number of participants who are not total positive
^a For participants with positive baseline ADA status, a post-baseline titer value that is ≥ 4 times higher than the baseline is considered as treatment-boosted ADA.	

A plot of plasma concentrations vs. analysis visits (months) will be created. Plasma concentrations of participants who are ADA total positive will be highlighted to explore the effect of ADA on PK of participants.

Pharmacokinetics

Plasma concentrations will be summarized descriptively for the PKAS in total at each analysis visit, using mean, SD, median, minimum, maximum, geometric mean, and coefficient of variation (CV).

Additional exploratory analysis may be performed after analysis of the data.

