11.5 Immunogenicity and PK Analyses

Additional details regarding immunogenicity and pharmacokinetic data analyses will be provided in the statistical analysis plan (SAP) prior to database lock.

Immunogenicity: A patient's overall ADA status will be reported as follows: ADA-negative, ADA-positive, ADA-inconclusive and Unevaluable samples.

Pharmacokinetics: Individual patient concentration-time data will be listed and summarized descriptively in tabular format.

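### Total Negative in SAP Table 1 is a residual row that labels some ADA-positive participants negative, and the pooled display mixes two kinds of baseline

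*SAP*

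**What the plan says.** SAP 4.4 sets one ADA baseline for everyone: "Baseline value is the last available value prior to the first administration of study drug in this study ISEE2009". Table 1 defines Total Positive as "Total number of participants who are either with a negative baseline and at least one post-baseline positive ADA status, OR treatment boosted positive". For the second route, "a post-baseline titer value that is ≥ 4 times higher than the baseline is considered as treatment-boosted ADA". Total Negative is the remainder: "Total number of participants who are not total positive".

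The ADA analysis set (ADAAS, SAP 3.4) is "all treated participants with at least one valid ADA result". Neither a valid baseline nor a valid post-baseline result is required.

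On display, "The following ADA incidences will be summarized over the ADAAS in total". SAP 4.1 makes prior-treatment cohorts the default for summaries but allows exceptions.

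Table 1 also has rows for baseline positive, post-baseline positive whatever the baseline, treatment boosted positive, and participants with both a valid baseline and a post-baseline result. A listing of ADA results is planned.

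Three places in the protocol bear on this:
- Section 3 (footnote i) and Section 7.6 describe the Month 1 sample as a drug-free baseline for Sham crossovers only.
- Section 11.5 calls for overall ADA status in four categories: "ADA-negative, ADA-positive, ADA-inconclusive and Unevaluable samples". SAP 4.4 recognises only positive and negative.
- Section 7.7 gives the effect of ADA on plasma concentration as the purpose of the PK sampling. The SAP's display for this is a plot of concentration by visit that highlights Total Positive participants.

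**The concern.** A residual category is safe only if everything left in it deserves the label. Here a participant can have a positive ADA sample, or no result after dosing, and still be reported as negative.

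The rule would be unremarkable if every baseline were pre-treatment, because a positive baseline without a boost would then be pre-existing reactivity. That holds for Sham crossovers. It does not hold for participants who received ACP in ISEE2008, where a positive Month 1 sample may be persisting ADA from that exposure. Pooling the two groups in one column hides which meaning applies.

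Immunogenicity is a secondary endpoint of a long-term safety study. The Total Positive and Total Negative rows are the ones most likely to be carried into a report as the immunogenicity result. The same classification decides who is highlighted in the PK plot, so unhighlighted participants may include ADA-positive people.

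**Working it through.** The documents state no ADA rate, and the study tests no hypotheses (SAP 2), so there is no planned figure to reproduce. The check applies Table 1 to every possible pattern and then gives a conditional count.

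**Step 1. Patterns.** Baseline is negative, positive or missing. Post-baseline is all negative, at least one positive, or no valid result. The 4-fold criterion applies only to a positive baseline. A missing baseline with no valid post-baseline result is outside the ADAAS. That leaves 3 + 4 + 2 = 9 patterns.

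| Baseline | Post-baseline | Table 1 label | Any positive sample? |
|---|---|---|---|
| Negative | Negative | Total Negative | No |
| Negative | Positive | Total Positive | Yes |
| Negative | No valid result | Total Negative | No (incomplete) |
| Positive | Negative | Total Negative | Yes |
| Positive | Positive, below 4-fold | Total Negative | Yes |
| Positive | Positive, 4-fold or more | Total Positive | Yes |
| Positive | No valid result | Total Negative | Yes (incomplete) |
| Missing | Negative | Total Negative | No (incomplete) |
| Missing | Positive | Total Negative | Yes (incomplete) |

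Seven patterns are Total Negative. One of them is a documented negative, four contain a positive sample, and two are negative on incomplete data.

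**Step 2. What the other rows recover.** Baseline positive minus treatment boosted positive gives the unboosted baseline positives, in total. Post-baseline positive minus those who were negative at baseline gives two groups combined: positive at baseline and again later, and baseline missing but positive later. Table 1 cannot separate these two. No row attributes anything to a cohort. The row for participants with both results is not named as a denominator.

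**Step 3. Illustration of size.** Assumptions, none given in the documents:
- The 280 participants split in proportion to the ISEE2008 treated arms, 225 ACP and 222 Sham (protocol 4.4). 280 × 225/447 = 141 ACP-experienced, and 280 − 141 = 139 Sham.
- A share q of the ACP-experienced is ADA-positive at the ISEE2009 baseline, and none of them is boosted.
- All Sham crossovers are negative at baseline.
- 2% of baseline-negative participants convert during ISEE2009.
- No results are missing.

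Positives labelled negative = 141q. Total Positive = 0.02 × (280 − 141q). Any positive = Total Positive + 141q. Percentages are of 280.

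| q | Positives in Total Negative | Total Positive | Any positive sample |
|---|---|---|---|
| 1% | 1.4 | 5.6 (2.0%) | 7.0 (2.5%) |
| 2% | 2.8 | 5.5 (2.0%) | 8.4 (3.0%) |
| 5% | 7.1 | 5.5 (2.0%) | 12.5 (4.5%) |
| 10% | 14.1 | 5.3 (1.9%) | 19.4 (6.9%) |

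The first count does not depend on the conversion rate. At q = 5%, conversion of 1% to 5% moves Total Positive from 1.0% to 4.9% and any positive from 3.5% to 7.4%. The gap stays at about 2.5 percentage points (7.1/280).

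**The case against.** The case for leaving the plan alone has substance. Measuring change against this study's own baseline, with a boost criterion, answers what happened during ISEE2009, and for Sham crossovers it is the right rule. SAP 4.1 allows exceptions to cohort display, and the SAP's change history anticipates few Total Positive participants. Month 1 sampling is a scheduled pre-injection procedure, so missing baselines should be rare. The study is descriptive, and the PK item is one exploratory plot without a formal comparison group. All of this limits the consequence. None of it makes the label correct.

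Four stronger readings might be inferred, and the documents do not support them:

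- *Everyone who turned ADA-positive in ISEE2008 is counted as negative.* No. Those with a 4-fold boost, and those negative at Month 1 who turn positive again, are Total Positive.
- *Unevaluable participants are counted as negative.* Participants with no valid result at all are outside the ADAAS. Only partly evaluable participants are affected. The absence of a row for protocol 11.5's two extra categories remains a gap.
- *ADA-positive people disappear from the report.* Most remain visible in the baseline positive and post-baseline positive rows and in the listing.
- *The reported ADA rate is halved.* Suppose 7 of 140 experienced participants are persistently positive and 7 of 140 naive participants convert. Total Positive is then 7/280 = 2.5%, but the post-baseline positive row prints 14/280 = 5%. The halving requires full persistence, no boosting and no new conversion in the experienced half. It also compares incidence with prevalence.

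**Conclusion.** The defect is real but narrow. That Table 1 mislabels the patterns above follows from its wording and needs no assumption about data. It affects the Total Positive/Total Negative summary and the highlighting in the PK plot. Pooling makes it harder to read, because baseline means pre-treatment in one group and on-treatment in the other. Pooling alone does not fix the direction of any bias.

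The size cannot be computed from the documents. The range of about 1 to 14 ADA-positive people labelled negative rests on an assumed 140 or so ACP-experienced participants and 1% to 10% unboosted positivity at the ISEE2009 baseline. If few Total Positive participants are expected, even the lower part of that range could matter to how the summary reads. This should be corrected before database lock. It does not threaten the primary endpoint.

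**What to change.** Amend SAP 4.4 as follows:

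1. Present Table 1 for Sham to ACP EM and for ACP to ACP EM, as well as in total.
2. Take treatment-emergent incidence on first exposure from Sham to ACP EM. For ACP to ACP EM, report prevalence, persistence and boosting relative to the ISEE2009 baseline. Use an ISEE2008 pre-dose baseline only if such samples exist; these documents do not show that they do.
3. Restrict Total Positive and Total Negative to participants with a valid baseline and at least one valid post-baseline result, and name the first row of Table 1 as the denominator. Define Total Negative as all results negative.
4. Add rows for baseline positive not boosted, missing baseline, and inconclusive or unevaluable, in line with protocol 11.5.
5. In the PK plot, highlight every ADA-positive sample or participant, not only Total Positive participants.

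The cost is SAP wording and a few more table rows and columns. No new samples are needed.
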